4.2 Secondary Objective

The secondary objectives are to assess:

- The percentages of subjects with on-treatment virologic failure.
- The percentages of subjects with post-treatment relapse.

Additional objectives are to assess pharmacokinetics and emergence/persistence of viral variants in these treatment regimens.

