5.2.3.2 Management of Immunosuppressant Agent Dosing

Drug-drug interaction studies have been conducted for ABT-493/ABT-530 co-administered with cyclosporine or tacrolimus and are detailed, along with the dosing recommendations during the Treatment Period as follows:

Dosing recommendations for tacrolimus management during treatment with ABT-493 and ABT-530 in this study are:

- For subjects who are initiating therapy with tacrolimus, the initial dose should be selected from the lower end of the recommended range as per the tacrolimus label (e.g., 0.10 mg/kg/day for adult liver transplant recipients).
- For subjects already taking tacrolimus, dosing should continue with close monitoring of tacrolimus trough levels and tacrolimus dose adjustment as needed.

Dosing recommendations for cyclosporine management during treatment with ABT-493 and ABT-530 in this study are:

[figure not shown]
• The dose of cyclosporine with ABT-493/ABT-530 (300/120 mg QD) should not exceed 100 mg once daily for entry into the study. If the cyclosporine maintenance dose needs to be increased to a total daily dose greater than 100 mg during the Treatment Period, discussion with the Therapeutic Area Medical Director should occur. Dosages of cyclosporine > 400 mg are not allowed during the Treatment Period.

For mTOR inhibitors, as the metabolic profile for both sirolimus and everolimus are similar to tacrolimus, management of sirolimus and everolimus will be similar to tacrolimus (refer to Section 3.0 for additional information).

- For subjects who are initiating therapy with sirolimus or everolimus, the initial
 dose should be selected from the lower end of the recommended range as per
 the sirolimus and everolimus labels.
- For subjects already taking sirolimus or everolimus, dosing should continue with close monitoring of drug trough levels and dose adjustment as needed.

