During this study, the dosing of tacrolimus, cyclosporine, sirolimus and everolimus will be informed by scheduled blood level testing. Tacrolimus, cyclosporine, sirolimus and everolimus blood level testing may be performed at any time during the study at the investigator's discretion. Where possible, it is recommended that CNI and mTOR medications be taken with study drugs in the morning with food. Based on in vitro drug-drug interaction studies, no potential interaction is expected with azathioprine, MMF and mycophenolic acid. Subjects may be on azathioprine, MMF, and/or mycophenolic acid as per the investigator's discretion. Monitoring of azathioprine, MMF, and/or mycophenolic acid levels beyond what is standard and clinically indicated is not required.

CNI dosing in the study is guided by the recommended dose reductions based on healthy volunteer data and modeled to achieve trough levels appropriate in the post-transplant setting. Clinical experience suggests some differences may be observed between patients

EudraCT 2015-005616-14

in relation to cyclosporine or tacrolimus dosing and associated trough levels. Therefore CNI and mTOR dosing will be guided by frequent trough level estimates, particularly during the first weeks of treatment administration, and by the investigators clinical experience in the management of CNI and mTOR medications in liver or renal transplant recipients.

On Day 1 of the Post-Treatment Period, it is recommended that the pre-study dose of immunosuppressants tacrolimus, sirolimus, everolimus and cyclosporine be resumed. Further modifications in tacrolimus, sirolimus, everolimus and cyclosporine dosing or dose frequency should be guided by measuring trough levels.

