8.1.6 Pharmacokinetic and Exposure-Response Analyses

Plasma concentrations of ABT-493 and ABT-530 and possible metabolites and pharmacokinetic parameter values for ABT-493 and ABT-530 will be tabulated for each subject and group. Blood concentrations of cyclosporine, tacrolimus, everolimus and sirolimus will be tabulated for each subject and group. Summary statistics will be computed for each time and visit.

Plasma concentration data from this study may be combined with data from other studies and analyzed using the following general methodology:

Population pharmacokinetic analyses will be performed using the actual sampling time relative to dosing. Pharmacokinetic models will be built using a non-linear mixed-effect modeling approach with the NONMEM software (version VII, or higher version). The structure of the starting pharmacokinetic model will be based on the pharmacokinetic analysis of data from previous studies. Apparent oral clearance (CL/F) and apparent volume of distribution (V/F) of the PK analytes will be the pharmacokinetic parameters of major interest in the NONMEM analyses. If necessary, other parameters, including the parameters describing absorption characteristics, may be fixed if useful in the analysis. The evaluation criteria described below will be used to examine the performance of different models.

• The objective function of the best model is significantly smaller than the alternative model(s).

[figure not shown]
- The observed and predicted concentrations from the preferred model are more randomly distributed across the line of unity (a straight line with zero intercept and a slope of one) than the alternative model(s).
- Visual inspection of model fits, standard errors of model parameters and change in inter-subject and intra-subject error.

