7.3 Prior, Concomitant and Post-Treatment Medications

A prior medication is defined as any medication taken prior to the date of the first dose of study drug (ABT-493/ABT-530). A concomitant medication is defined as any medication that started prior to the date of the first dose of study drug and continued to be taken on or after the first dose of study drug or any medication that started on or after the date of the first dose of study drug, but not after the date of the last dose of study drug. A post-treatment medication for the treatment of HCV is defined as any medication taken on or after the last dose of study drug and entered as "Post-treatment HCV medications" on the eCRF.

The number and percentage of subjects taking prior medications, concomitant medications, and post-treatment HCV medications will be summarized by generic drug name based on the WHO Drug Dictionary. The prior HCV medications taken by the treatment experienced subjects will be summarized separately from other prior medications.

The number and percentage of subjects taking concomitant immunosuppressant medications will be summarized separately from other concomitant medications.

The number and percentage of subjects with immunosuppressant medication dosage increase and decrease, respectively, at each post-baseline visit in the treatment period will be summarized by each immunosuppressant medication as captured on the "Immunosuppression Regimen Dosing Diary" eCRF (i.e., Cyclosporine, Sirolimus, Everolimus and Tacrolimus).

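### Troughs of tacrolimus, sirolimus and everolimus are summarized without the doses that produced them, so trough-guided dosing can make the effect of study drug look smaller than it is

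*Protocol*

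**What the plan says.** **Dosing.** Protocol 5.2.3.2 states that "the dosing of tacrolimus, cyclosporine, sirolimus and everolimus will be informed by scheduled blood level testing". Of tacrolimus it says: "For subjects already taking tacrolimus, dosing should continue with close monitoring of tacrolimus trough levels and tacrolimus dose adjustment as needed". The mTOR inhibitors are handled by analogy: "as the metabolic profile for both sirolimus and everolimus are similar to tacrolimus, management of sirolimus and everolimus will be similar to tacrolimus". The same section expects most of the adjustment early: "CNI and mTOR dosing will be guided by frequent trough level estimates, particularly" in the first weeks of treatment.

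**Concentration summary.** The synopsis and Protocol 5.3.6 list immunosuppressant concentrations among the pharmacokinetic variables. Protocol 8.1.6 then says "Blood concentrations of cyclosporine, tacrolimus, everolimus and sirolimus will be tabulated for each subject and group", followed by summary statistics for each time and visit. The SAP has no section on drug concentrations.

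**Dose summary.** SAP 7.3 will report, for each of the four agents, "The number and percentage of subjects with immunosuppressant medication dosage increase and decrease, respectively, at each post-baseline visit in the treatment period".

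**Objective.** Protocol 4.2 says: "Additional objectives are to assess pharmacokinetics and emergence/persistence of viral variants in these treatment regimens".

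**Data collected.** Diaries record each dose with strength, date and time (Protocol 5.1.2). For each level drawn, the eCRF takes the result, the sampling date and time, and the dosing details (Protocol 5.3.1.1). Levels are scheduled at Screening, Day 1 and every treatment visit (Appendix C), and from Post-Treatment Day 3 to Week 4 (Appendix D).

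**The concern.** When a dose is adjusted in response to a level, the level no longer measures the interaction alone. A mean trough that stays flat after study drug starts could mean that there was no interaction, or that there was one and investigators corrected for it. A table of concentrations by visit cannot separate the two.

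Protocol 3.2 names altered tacrolimus, sirolimus and everolimus exposure among the risks. At stake is whether the study report can describe the size of that effect in transplant recipients. For tacrolimus the protocol has a Phase 1 estimate, from a single 1 mg dose in healthy subjects. For sirolimus and everolimus these documents report no interaction study and rely on the resemblance to tacrolimus. An understated effect would be hardest to notice for those two agents.

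**Working it through.** The plan gives no figure of its own to reproduce here. The check shows what the planned tables would report if the effect on tacrolimus were the size the protocol cites.

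**Inputs**
- R = 1.50, the on-treatment to baseline exposure ratio for tacrolimus (Protocol 3.0, Study M13-592).
- R = 1.14, the upper figure for cyclosporine, from the 100 mg study (Protocol 3.0, Study M13-584).
- f, the share of the effect titrated away on the log scale. The documents do not give it, so it is varied from 0 to 1.
- Assumed: concentration proportional to dose, and steady state after any dose change.

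**Formulas**
- Dose ratio = R^(−f).
- Raw concentration ratio = R × dose ratio = R^(1−f).
- Dose-normalized ratio = raw ratio ÷ dose ratio = R.

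The raw geometric mean ratio is the same if, instead, a fraction f of subjects has the dose multiplied by 1/R (for tacrolimus 2/3, a cut of one third) and the rest have no change.

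| f | Tacrolimus dose ratio | Tacrolimus raw ratio | Tacrolimus dose-normalized ratio | Cyclosporine raw ratio |
|---|---|---|---|---|
| 0 | 1.00 | 1.50 | 1.50 | 1.14 |
| 0.25 | 0.90 | 1.36 | 1.50 | 1.10 |
| 0.50 | 0.82 | 1.22 | 1.50 | 1.07 |
| 0.75 | 0.74 | 1.11 | 1.50 | 1.03 |
| 1 | 0.67 | 1.00 | 1.50 | 1.00 |

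The constant 1.50 follows from the assumptions by construction. It shows what dose normalization is meant to recover and is not a forecast of the trial's result.

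**Do the SAP's dose-change counts close the gap?** Suppose the two planned tables show a raw ratio of 1.225 and a dose decrease in half the subjects. If each decrease multiplied the dose by 0.667, the underlying ratio is 1.225 ÷ √0.667 = 1.50. If each multiplied it by 0.904, the ratio is 1.225 ÷ √0.904 = 1.29. Both tables would look the same in the two cases. The counts point the right way but do not fix the size.

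**Does the population model close it?** Protocol 8.1.6 models clearance and volume of the pharmacokinetic analytes with concomitant medication as a covariate. The analytes appear to be ABT-493 and ABT-530, so this addresses the effect of immunosuppressants on study drug, which is the reverse direction.

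**The case against.** The strongest reply is that the plan already shows the signal. Under titration, a real interaction appears in SAP 7.3 as an excess of dose decreases, and better monitoring makes that excess clearer. This stands. A reader might infer that only raw concentrations are summarized, or that the interaction is hidden altogether, and the SAP does not support either. What is missing is the magnitude.

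A reader might also infer that the trial fails an objective to measure this interaction. No objective says so. Protocol 4.2 and SAP 4.1 speak of pharmacokinetics in general, and the footnote to Protocol Table 2 says the levels are measured locally for dose management. Protocol 3.2 places altered immunosuppressant exposure under other risks, mitigated by monitoring, and does not rank it as a main one. For the safety question of whether levels stayed acceptable, raw troughs by visit are the right table and should remain.

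Nor can this trial be called the only clinical source for sirolimus and everolimus. Protocol 3.0 refers to the Investigator's Brochure for detailed interaction data, and that is not part of these documents.

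Masking need not be complete, since Day 3 and Week 1 troughs may precede dose changes. For cyclosporine there is little to mask.

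The proposed ratio has limits of its own. From Day 1, study drug and immunosuppressants are to be taken together with food (Protocol 5.5.4), so a before-and-after ratio may also pick up changes in timing or food. Differences between local assays cancel only if the subject's laboratory stays the same and any bias is proportional. Subjects who start an agent during treatment have no baseline.

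These points narrow the concern. They do not give the raw-trough table a way to show the size of the effect.

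**Conclusion.** The concern holds in a limited form. Doses respond to troughs, the planned concentration summary ignores dose, and the dose-change counts give direction and frequency without size. With the protocol's own 50% tacrolimus increase, raw troughs could show anything from the full 1.50 to 1.00, depending on an amount of titration that neither planned table reveals. That range rests on proportional pharmacokinetics, on steady state, and on carrying a single-dose healthy-volunteer estimate over to maintenance troughs.

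The point applies to tacrolimus, and to sirolimus and everolimus if they behave alike, as the protocol supposes. It is a gap in a descriptive pharmacokinetic analysis. SVR12, its 86% threshold and the other efficacy conclusions are unaffected. It is worth correcting because the correction is cheap and the data are already collected. The general allowance in Protocol 8.1.6 for further analyses would permit the table but does not prespecify it.

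**What to change.** In Protocol 8.1.6 and in the SAP, keep the raw troughs and the dose-change counts, and add one descriptive table per agent:

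- **Measure:** dose-normalized trough, that is, trough divided by the total daily dose preceding it.
- **Summary:** within-subject ratio to the pre-dose Screening/Day 1 value, as a geometric mean ratio with 95% CI.
- **Visits:** each treatment visit, and each post-treatment visit through Post-Treatment Week 4.
- **Agents:** tacrolimus, sirolimus and everolimus, with cyclosporine for completeness.
- **Subjects:** those with a pre-treatment trough on the same agent.
- **Notes to the table:** the assumptions of proportional pharmacokinetics, steady state after a dose change and an unchanged local laboratory, and the caution that dose timing and food may also change from Day 1.

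The cost is programming four tables from data already in the eCRF. The sirolimus and everolimus groups may be small, so their intervals may be wide. The change is to the analysis only and alters no dose, monitoring schedule or clinical rule.

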8.2 Determination of Sample Size

It is planned to enroll approximately 90 subjects with a minimum of 15 post-renal transplant subjects and a maximum of approximately 50 subjects with HCV genotype 1 infection. The primary efficacy endpoint of SVR₁₂ will be assessed for the ITT population. For the primary efficacy endpoint of SVR₁₂, with a sample size of 90 subjects and assuming that 96% of the subjects will achieve SVR₁₂, this study has greater than 90% power to show non-inferiority to the historical SVR₁₂ rate of 94% (based on the lower bound of a normal approximation of a single binomial proportion confidence interval being above a threshold of 86%) using a one-sample test for superiority using EAST 6.3.

No adjustment for dropouts is applicable because subjects who do not have data at Post-Treatment Week 12 (after imputing) are counted as failures for SVR₁₂.

8.2.1 Justification of Success Criterion and Non-Inferiority Margin for SVR₁₂

The primary efficacy endpoint analysis of SVR₁₂ is a non-inferiority test of the SVR₁₂ rate in this study to the historical SVR₁₂ rate of 94% (based on the lower bound of a normal approximation of a single binomial proportion confidence interval being above a threshold of 86%) using a one-sample test for superiority.

The 86% threshold was established by applying an 8% non-inferiority margin to a historical SVR₁₂ rate of 94%.

The 8% non-inferiority margin is based on the paucity of data in non-GT1 liver transplant recipients and renal transplant recipients regardless of genotype and the potential benefit of a RBV-free regimen.

- Most data published on the post-transplant population to date, including the studies that were used to establish the historical control rate for this study, are in GT1 subjects who have received a liver transplant.
- The current standard-of-care regimens used for historical comparison all include RBV. Given the ABT-493/ABT-530 regimen is RBV-sparing, a slightly wider non-inferiority margin compared to the margin used in other AbbVie Phase 3 studies with ABT-494/ABT-530 was considered, as a small decrement in efficacy may be outweighed by an improvement in safety offered with the avoidance of RBV in a patient population more susceptible to RBV-related toxicity.

abbvie ABT-493/ABT-530 M13-596 Protocol Amendment 2 EudraCT 2015-005616-14

9.0 **Ethics**

9.1 Independent Ethics Committee (IEC) or Institutional Review Board (IRB)

[figure not shown]
Good Clinical Practice (GCP) requires that the clinical protocol, any protocol amendments, the Investigator's Brochure, the informed consent and all other forms of subject information related to the study (e.g., advertisements used to recruit subjects) and any other necessary documents be reviewed by an IEC/IRB. The IEC/IRB will review the ethical, scientific and medical appropriateness of the study before it is conducted. IEC/IRB approval of the protocol, informed consent and subject information and/or advertising, as relevant, will be obtained prior to the authorization of drug shipment to a study site.

Any amendments to the protocol will require IEC/IRB approval prior to implementation of any changes made to the study design. The investigator will be required to submit, maintain and archive study essential documents according to ICH GCP.

Any serious adverse events that meet the reporting criteria, as dictated by local regulations, will be reported to both responsible Ethics Committees and Regulatory Agencies, as required by local regulations. During the conduct of the study, the investigator should promptly provide written reports (e.g., ICH Expedited Reports, and any additional reports required by local regulations) to the IEC/IRB of any changes that affect the conduct of the study and/or increase the risk to subjects. Written documentation of the submission to the IEC/IRB should also be provided to AbbVie.

9.2 **Ethical Conduct of the Study**

The study will be conducted in accordance with the protocol, International Conference on Harmonization (ICH) guidelines, applicable regulations and guidelines governing clinical study conduct and the ethical principles that have their origin in the Declaration of Helsinki. Responsibilities of the clinical investigator are specified in Appendix A.

9.3 Subject Information and Consent

The investigator or his/her representative will explain the nature of the study to the subject, and answer all questions regarding this study. Prior to any study-related screening procedures being performed on the subject, the informed consent statement will be reviewed and signed and dated by the subject, the person who administered the informed consent, and any other signatories according to local requirements. A copy of the informed consent form will be given to the subject and the original will be placed in the subject's medical record. An entry must also be made in the subject's dated source documents to confirm that informed consent was obtained prior to any study-related procedures and that the subject received a signed copy.

Information regarding incentives for subjects and information regarding provisions for treating and/or compensating subjects who are harmed as a consequence of participation in the study can be found in the informed consent form.

The optional pharmacogenetic and intensive PK analysis will only be performed if the subject has voluntarily signed and dated the IRB/IEC approved pharmacogenetic informed consent and intensive PK informed consent respectively, after the nature of the testing has been explained and the subject has had an opportunity to ask questions. The subject must provide consent specific to pharmacogenetic testing and intensive PK before the testing is performed. If the subject does not consent to the additional pharmacogenetic and/or intensive PK testing it will not impact the subject's participation in the study.

In the event a subject withdraws from the main study, optional pharmacogenetic exploratory research samples will continue to be stored and analyzed unless the subject specifically withdraws consent for the optional samples. If consent is withdrawn for the optional sampling, the subject must inform their study doctor, and once AbbVie is informed, the optional samples will be destroyed. However, if the subject withdraws his/her consent and the samples have already been tested, those results will still remain as part of the overall research data.

abbvie ABT-493/ABT-530 M13-596 Protocol Amendment 2 EudraCT 2015-005616-14

10.0 **Source Documents and Case Report Form** Completion

10.1 **Source Documents**

Source documents are defined as original documents, data and records. This may include hospital records, clinical and office charts, laboratory data/information, subjects' diaries or evaluation checklists, pharmacy dispensing and other records, recorded data from automated instruments, microfiches, photographic negatives, microfilm or magnetic media, and/or x-rays. Data collected during this study must be recorded on the appropriate source documents.

[figure not shown]
The investigator(s)/institution(s) will permit study-related monitoring, audits, IEC/IRB review, and regulatory inspection(s), providing direct access to source data documents.

10.2 **Case Report Forms**

Case report forms (CRF) must be completed for each subject screened/enrolled in this study. These forms will be used to transmit information collected during the study to AbbVie and regulatory authorities, as applicable. The CRF data for this study are being collected with an electronic data capture (EDC) system called Rave® provided by the technology vendor Medidata Solutions Incorporated, NY, USA. The EDC system and the study-specific electronic case report forms (eCRFs) will comply with Title 21 CFR Part 11. The documentation related to the validation of the EDC system is available through the vendor, Medidata, while the validation of the study-specific eCRFs will be conducted by AbbVie and will be maintained in the Trial Master File at AbbVie.

The investigator will document subject data in his/her own subject files. These subject files will serve as source data for the study. All eCRF data required by this protocol will be recorded by investigative site personnel in the EDC system. All data entered into the eCRF will be supported by source documentation.

The investigator or an authorized member of the investigator's staff will make any necessary corrections to the eCRF. All change information, including the date and person

performing the corrections, will be available via the audit trail, which is part of the EDC system. For any correction, a reason for the alteration will be provided. The eCRFs will be reviewed periodically for completeness, legibility, and acceptability by AbbVie personnel (or their representatives). AbbVie (or their representatives) will also be allowed access to all source documents pertinent to the study in order to verify eCRF entries. The principal investigator will review the eCRFs for completeness and accuracy and provide his or her electronic signature and date to eCRFs as evidence thereof.

[figure not shown]
Medidata will provide access to the EDC system for the duration of the trial through a password-protected method of internet access. Such access will be removed from investigator sites at the end of the site's participation in the study. Data from the EDC system will be archived on appropriate data media (CD-ROM, etc.) and provided to the investigator at that time as a durable record of the site's eCRF data. It will be possible for the investigator to make paper printouts from that media.

